**Sponsored by:**

**National Institute of Drug Abuse (NIDA) at the National Institutes of Health (NIH)**

**R34 DA 051933**

**Protocol Chair: [name]**

**Version 3.0**

**October 1, 2023**

## ABSTRACT

Injection drug use is the primary driver of the HIV epidemic in Southeast Asia. In 2017, the HIV prevalence among people who inject drugs (PWID) in Southeast Asia was 15%. PWID, most of whom have opiate use disorder (OUD), have low rates of HIV testing, retention in care, antiretroviral therapy (ART) initiation, and viral suppression. PWID also experience high rates of HIV-related and all-cause mortality. Common mental disorders (CMDs), including depressive, anxiety, and stress-related illnesses, occur in 40-50% of PLWH and OUD and are strongly associated with negative outcomes for HIV patients, including worsening course of HIV, more rapid progression to AIDS, increased ART non-adherence, and increased mortality rates.

To respond to the great need for mental health treatment in low- and middle-income countries, the global mental health field has focused on developing task-shifting and integration approaches that equip non-specialists to deliver evidence-based mental health interventions at scale. However, such task shifting interventions to address CMDs have received limited attention in Southeast Asia among OUD. Vietnam, with its high prevalence of PLWH and OUD, its integration of methadone maintenance therapy with HIV care, and its priority for developing CMD care for this population, is an ideal setting to evaluate task-shifting mental health approaches to address CMDs and improve HIV care outcomes.

The Friendship Bench (FB) is a feasible and effective task-shifting mental health intervention designed for low-resource settings that is a strong candidate to address CMDs in this population. FB is a problem solving therapy-based intervention with demonstrated effectiveness treating CMDs among primary care patients when delivered by lay counselors. Lay counselors may effectively deliver FB to PLWH with OUD, but CMD may prove more difficult to treat in patients with OUD and require professionally trained counselors to be effective.

Our objective in this proposal is to complete a pilot randomized trial of 75 patients from 4 MMT clinics in Hanoi. Our specific aims are: 1) To adapt the Friendship Bench (FB) protocol to be optimized for PLWH and OUD in Vietnam; and 2) To evaluate the feasibility, fidelity, and acceptability of the adapted FB as well as preliminary indicators of its impact in improving CMDs and HIV care and drug use treatment outcomes. The Friendship Bench approach has the potential to make an important contribution to address CMDs and reduce barriers to HIV treatment success among PLWH with OUD, a critical population driving the HIV epidemic in Vietnam and many Southeast Asian countries. This proposal will generate critical evidence for designing a fully powered clinical trial to test our adapted FB protocol in improving HIV, mental health, and drug use treatment outcomes for this vulnerable population.

## HISTORY OF PROTOCOL CHANGES

### Version 1.0, 21 May 2020

- None to date.

### Version 2.0, 23 September 2020

- Addition of formative phase in-depth interviews and focus groups to Section 3, Aim 1.

### Version 3.0, 1 October 2023

- Updated outcome measures.

## GLOSSARY OF TERMS/ACRONYMS

AIDS	Acquired Immunodeficiency Syndrome
ART	Antiretroviral Therapy
CDC	Center for Disease Control
CMD	Common Mental Disorder
DASS-21	Depression, Anxiety, and Stress Scale -21
EUC	Enhanced Usual Care
FB	Friendship Bench
GEE	generalized estimating equation
HIV	Human Immunodeficiency Virus
IRB	Institutional Review Board
LMIC	Low- and Middle-Income Country
MINI	Mini International Neuropsychiatric Interview
MMT	Methadone Maintenance Therapy
MOH	Ministry of Health
NIDA	National Institute of Drug Abuse
NIH	National Institutes of Health
OHRP	Office for Human Research Protections
OUD	Opiate Use Disorder
PI	Principal Investigator
PLWH	People Living with HIV
PST	Problem-solving Therapy
PWID	People Who Inject Drugs
RCT	Randomized Clinical Trial
SAE	Serious Adverse Event
UNC	University of North Carolina

## 1.0 INTRODUCTION

This project will adapt and pilot a feasible and effective problem-solving therapy designed for low-resource settings to address common mental disorders like depression and anxiety – the Friendship Bench – in a Vietnamese population of individuals living with HIV who also have opiate use disorder. The Friendship Bench approach has the potential to make an important contribution to address CMDs and reduce barriers to HIV treatment success among PLWH with OUD, a critical population driving the HIV epidemic in Vietnam and many Southeast Asian countries. This proposal will generate critical evidence for designing a fully powered clinical trial to test our adapted FB protocol in improving HIV, mental health, and drug use treatment outcomes for this vulnerable population.

### 1.1 Background and Literature Review

Injection drug use is the primary driver of the HIV epidemic in Southeast Asia. Parenteral exposure to infected blood is one of the most efficient means of HIV transmission, which has resulted in rapid and uncontrolled HIV epidemics among PWID. In Southeast Asia, as in many other LMICs, HIV prevalence among people who inject drugs (PWID) is several times higher than HIV prevalence in the general population and involves users from all genders. In 2017, the HIV prevalence among PWID in Southeast and Central Asia was 15% and 11%, respectively. PWID, most of whom have OUD, who are living with HIV have low rates of retention in care, antiretroviral therapy (ART) initiation, and viral suppression, reflecting the marginalized and stigmatized nature of this group. PWID also experience high rates of HIV-related and all-cause mortality at all stages of the HIV care continuum. Policy makers have identified the urgent need to increase the reach and effectiveness of HIV treatment programs in this population.

Common mental disorder (CMDs), a collective term referring to depressive, anxiety, and stress-related disorders, are highly prevalent among PLWH and OUD. Depression is the most common psychiatric comorbidity – and one of the most common comorbidities overall – among adults living with HIV worldwide. Depression affects an estimated 20-40% of people living with HIV. Anxiety or traumatic stress disorders are also common, occurring in 10-20% of HIV-infected individuals, and are often comorbid with MDD in this population. Compared to the general population of people living with HIV, PWID living with HIV are even more prone to CMDs due to economic hardship, incarceration, and HIV and drug related stigmatization and discrimination. One study reported that the prevalence of moderate to severe depressive and anxious symptoms among PWID living with HIV was 69% with up to 63% meeting diagnostic criteria for a depressive disorder.

Despite serious consequences of mental illness on health and HIV progression, mental illness remains under-diagnosed and under-treated in HIV populations, especially in LMIC countries, such as many countries in Southeast Asia. In LMICs, between 76% and 85% of people with mental disorders receive no treatment for their disorder, with an even greater risk for under treatment for those with HIV and coexisting substance use. Collectively, the cluster of diagnoses – HIV, common mental disorders, and substance abuse disorders – has emerged as a distinct clinical condition wherein patients experience a complex set of medical, psychological and social complications that need to be tackled through integrated care. Treatment for mental health conditions is a critical step in improving the emotional and physical well-being of HIV-infected PWID. While appropriate management tools are increasingly available, healthcare services for CMDs remain scarce in LMICs.

IRB# 20-1689

Protocol v3.0 2023-10-01

Feasible and effective task-shifting mental health interventions are key to addressing this need. To respond to the high burden of mental disorders globally and the vast unmet need for mental health treatment in low and middle income countries, the global mental health field has focused on developing task-shifting and integration approaches that equip non-specialists to deliver evidence-based mental health interventions at scale. Such approaches will be critical to respond to the large unmet need for mental health treatment among PLWH/OUD. However, such task-shifting interventions to address CMDs among PLWH and OUD have received limited testing in Southeast Asia.

## 1.2 Study Rationale

Vietnam is an ideal setting to evaluate the potential of task-shifting mental health approaches to address CMDs and improve HIV care outcomes among PLWH and OUD. First, as with other countries in Southeast Asia, the HIV epidemic in Vietnam is heavily concentrated among those with OUD (primarily heroin). Vietnam has been identified as one of six countries accounting for half of the global population of PWID, with the prevalence of HIV among this group ranging from 15-30%. Second, the Vietnam Ministry of Health (MOH) has dramatically expanded methadone maintenance therapy (MMT) clinics for those with OUD as well as integrated MMT/ART care for PLWH with OUD; this integrated care model, providing HIV treatment in the MMT clinics where most individuals with OUD receive care, provides an ideal platform to additionally address CMDs. Third, the Vietnam MOH has prioritized development of CMD care for PLWH and OUD. Nevertheless, substantial barriers to care exist. Key challenges to mental health treatment in the general population in Vietnam include the lack of mental health legislation and of personnel and psychiatric facilities, and few mental health treatment resources are currently available to this highly stigmatized population.

The Friendship Bench (FB) is a feasible and effective task-shifting mental health intervention designed for low-resource settings that is a strong candidate to address CMDs in this population. FB is a problem solving therapy-based intervention with demonstrated effectiveness in addressing CMDs among primary care patients when delivered by lay counselors. FB is designed to respond to CMDs generally rather than one psychiatric diagnosis specifically, and to meet the needs of low-resource settings with few mental health specialists.

Lay counselors may prove effective in delivering FB to PLWH with OUD; indeed, in other work we have demonstrated the effectiveness of peer counselors in improving ART adherence in this population. That said, CMDs may prove more difficult to treat in a population with OUD than among primary care patients, requiring the higher skill level of professional counselors for FB to be effective with this key population. A number of health care professionals in Vietnam have training in counseling, and the MOH could invest in expanding this cadre if evidence suggests that the higher level of training is critical. However, if lay counselors are equally effective then their deployment would be less expensive.

Our **objective** is to complete a pilot randomized trial of 75 patients from 4 MMT clinics where we have worked successfully in the past. We will compare FB delivered by professional counselors and FB delivered by lay counselors vs. enhanced usual care to improve CMDs and HIV care outcomes among PLWH and OUD in Vietnam. This work will

generate critical data to inform a fully powered R01 trial. We **hypothesize** that adapted FB will be acceptable to patients and providers, prove feasible to integrate into MMT clinics, be delivered with fidelity, and demonstrate preliminary indications of impact with both counselor groups.

## 2.0 HYPOTHESES AND STUDY OBJECTIVES

### 2.1 Hypotheses

There are not specific hypotheses for this pilot study. Our **objective** in this proposal is to complete a pilot randomized trial of 75 patients from 4 MMT clinics in Hanoi.

We will adapt the evidence-based FB intervention for the specific needs of adult PLWH and OUD in Vietnam (Aim 1).

We will then pilot the adapted FB protocol in a three-armed randomized controlled pilot trial (*professional counselors, lay counselors, or enhanced usual care*) with 75 adult HIV patients with OUD. We will assess feasibility and acceptability of the adapted FB protocol through semi-structured interviews with patients and providers, while evaluating fidelity of delivery and preliminary indicators of impact in improving HIV (primary outcome in subsequent R01), mental health (secondary), and drug use treatment (secondary) outcomes (Aim 2)

### 2.2 Study Objectives

**AIM 1:** To adapt the proven Friendship Bench (FB) protocol to be optimized for PLWH and OUD in Vietnam.

**Key outcome of Aim 1.** The primary outcome of Aim 1 will be the finalized revised FB protocol that is adapted for PLWH and OUD in Vietnam.

**AIM 2:** To assess the feasibility, fidelity, and acceptability of the adapted FB as well as preliminary indicators of its impact in improving CMD and engagement in HIV care and drug use treatment via a small three-arm individually randomized trial, comparing FB by professional counselors to FB by lay counselors to enhanced usual care for PLWH and OUD with CMDs.

The **primary outcomes** of the pilot trial will be the feasibility, acceptability, and fidelity of delivery of the adapted FB protocol. **Secondary outcomes** will include preliminary indicators of impact of the adapted FB protocol in improving HIV-related outcomes (eventual R01 primary outcomes) and MMT and mental health outcomes (eventual R01 secondary outcomes).

## 3.0 METHODOLOGY

**AIM 1: Adaptation process: ADAPT-ITT.** Our team has an established manual for FB, and procedures for adapting the FB manual for specific settings and contexts (e.g., our protocols for adapting for HIV, perinatal, and noncommunicable disease settings in our prior work in Malawi). We will engage in a collaborative process with the full range of stakeholders who will use the manual to ensure contextual and patient relevance.

During the first 6 months of the project, we will follow the ADAPT-ITT model to adapt the FB protocol for our population and outcomes. ADAPT-ITT consists of 8 steps (**Figure**). The first 2 steps, Assessment of needs of the patient population and Decision about the evidence-based intervention to select, as summarized in the Specific Aims and Significance sections, have guided the development of this proposal and the selection of FB to address CMDs among patients with HIV on MMT.

Step 3 (Adaptation) involves presenting FB to members of the target population and soliciting responses, encompasses feedback from potential clients and counselors. We will present the FB protocol to 5 distinct groups: patients (in-depth individual interviews, n=16), family members of patients (in-depth individual interviews, n=16), HIV/MMT clinicians and staff (2 focus groups, n=10 total), and directors of HIV/MMT clinics (individual interviews, n=6). We will solicit their feedback through in-depth interviews and focus group discussions.

ADAPT-ITT Model Steps	
1	Assess population needs
2	Decide on intervention
3	Adaptation with stakeholders
4	Production of adapted protocol
5	Topical expert input
6	Integration of expert input
7	Training
8	Testing of adapted protocol

Wingood et al. JAIDS 2008

Specific inclusion criteria and study activities for each group:

- HIV/MMT patients (n=16): Patients receiving both HIV and MMT care, who also have elevated symptoms of depression, anxiety, or stress on the DASS-21: a depression subscale score  $\geq 7$ , an anxiety subscale score  $\geq 6$ , and/or a stress subscale score  $\geq 10$ . These cut-offs indicate at least a moderate severity of symptomatology (see Trial Phase below). We will purposively sample participants to enroll at least 4 patients with depression, at least 4 with anxiety, and at least 4 with stress (one individual can help meet more than one of these targets if they are elevated on more than one domain). These individuals will complete one-time individual in-depth interviews lasting approximately one hour.
- Family members (n=16): We will ask each patient if we may speak with their spouse, mother, or other primary household caregiver. We will ask if they have disclosed their HIV and injection drug use status to that family member, and will only approach the family member if the patient has disclosed to them and is willing for us to talk with them about these issues. These individuals will complete one-time individual in-depth interviews lasting approximately one hour.
- HIV/MMT clinic providers and staff (2 focus groups, up to n=10 total): We will invite HIV/MMT clinic providers and staff who have meaningful involvement in the delivery of care for participating patients. These individuals will participate in a one-time focus group lasting approximately one and a half hours.
- HIV/MMT clinic directors (n=6): We will invite directors of the HIV/MMT clinics, CDC Hanoi, DOH Hanoi to complete individual interviews lasting approximately one hour.

[figure not shown]
**Data collection and storage.** All in-depth interviews and focus group discussions will be audio-recorded, stored on a secure server, transcribed and translated for analysis.

In step 4 (Production), this patient and provider feedback will be incorporated into a first draft of the adapted FB protocol. Steps 5 and 6 involve solicitation and integration of topical expert input. We will identify three individuals external to the study team with expertise in FB and in behavioral interventions for people with HIV and/or OUD to review the adapted

protocol. Feedback from this review will inform the development of the next draft of the protocol. In steps 7 and 8, an interventionist will be trained and this second draft will be piloted with 5 eligible patients to further refine session content. The process will culminate with a final version of the adapted FB protocol that will be ready for formal evaluation in Aim 2 in a three-arm pilot study.

**AIM 2: To assess the feasibility, fidelity, and acceptability of the adapted FB as well as preliminary indicators of its impact in improving CMD and engagement in HIV care and drug use treatment via a small three-arm individually randomized trial, comparing FB by professional counselors to FB by lay counselors to enhanced usual care for PLWH and OUD with CMDs.**

**Study Design.** We will complete a pilot trial in which we will randomize 75 eligible patients to either the FB by a professional counselor (n=25), or FB by a lay counselor (n=25), or enhanced usual care (n=25). Patients will be enrolled from 4 MMT clinics under CDC Hanoi jurisdiction and with which we have previous successful collaborations. Patients meeting full eligibility criteria (see below) will be invited to provide written informed consent to participate in the study. As a pragmatic effectiveness trial, the purpose of the eventual R01 will be to compare the effectiveness of the adapted FB protocol delivered by a professional counselor and delivered by a lay counselor relative to enhanced usual care in improving HIV/MMT care engagement and outcomes (primary outcomes for the future trial). Therefore in this pilot, consenting participants will be individually randomized in the same way, to one of those three arms (described below).

[figure not shown]

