## 4.0 ANALYSIS

**Statistical Analysis.** Feasibility, acceptability, and fidelity will be evaluated using descriptive statistics. We will compare mean fidelity scores between the professional FB and lay FB counselors using an intent-to-treat approach, using a robust variance estimator to account for multiple observations per counselor. Means and proportions for HIV-related and mental health outcomes will be compared between arms using an intent-to-treat analysis approach.

We will evaluate effectiveness measures comparing professional counselors to enhanced usual care and lay counselors to enhanced usual care. Considering the purpose of this small pilot trial, our focus will be on estimating effect size and precision rather than statistical significance and hypothesis testing. To take advantage of the repeated-measures nature of the outcome data, we will also fit generalized estimating equation (GEE) regression models, using a link appropriate for each outcome (i.e. identity link for continuous variables and log link for binary variables), to simultaneously examine differences in outcomes at 6 weeks, 3 months, 6 months and 12 months between the arms. Given the relatively small sample size, it is possible that important predictors of outcome (such as baseline mental health symptom severity or time in HIV care) could end up being unbalanced between arms; if this is the case we will conduct secondary regression analyses adjusting for the unbalanced potential confounder.

In **secondary analyses**, we will examine whether HIV-related, MMT, and mental health outcomes vary by proportion of FB sessions attended and by number of elevated symptom domains at baseline (depression, anxiety, and/or post-traumatic stress).

In **moderation analyses**, we will explore whether severity of illness (duration; symptom severity; family history) modifies any preliminary evidence of efficacy in primary outcomes, while recognizing that a pilot trial is not designed to be powered to statistically test modification hypotheses.

**Missing data.** Every effort will be made to minimize missing data, including collecting detailed locator information for the participant as well as for up to three individuals who could help reach the participant should they drop out of contact. However, some missing

IRB# 20-1689

Protocol v3.0 2023-10-01

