#### *5.1.2 Confidentiality, Risks, and Risk Minimization*

Breach of confidentiality: There is always the possibility of a breach of confidentiality when conducting research. Disclosure of medical or other personal information about participants, particularly HIV, substance use disorder, and mental health status, may result in negative stigma being associated with the individual and/or family. Our research team is very aware of the need for absolute confidentiality and has extensive experience in dealing with highly sensitive personal medical and family information. While we acknowledge that a breach of confidentiality is possible, we anticipate that the likelihood is very low because of the precautions that will be taken to protect confidentiality. Research data will be coded (with identifiers removed). The linking file that connects the codes to individual identities will be securely stored by the study team. Research data will be stored securely on password-protected machines or servers or in locked cabinets, with access restricted to study staff.

For qualitative interviews: recording devices will be locked up when not in use, and audio files and transcripts will be stored securely on password-protected machines or servers with access restricted to study staff. Careful attention will be paid to anonymizing transcripts (removing potentially self-identifying references) and aggregating responses before sharing them with the full investigator team to prevent any potential for identification.

Risk of sense of coercion to participate: As addressed under 2(a) above, the informed consent process will emphasize that the provider is free to participate or not; a decision not to participate will have no negative impact on his or her employment, evaluation, or anything else related to the workplace; and the provider is free to end participation at any time. For patients, the informed consent process will emphasize that the patient is free to participate or not; a decision not to participate will have no negative impact on any aspect of his or her clinical care; and the patient is free to end participation at any time.

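### The Aim 1 check made before a relative is approached covers HIV and injection drug use but not mental health, so the contact can let the relative infer the patient's mental health status

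*Combined protocol and SAP*

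**What the plan says.** Section 3.0, Aim 1, describes the patients to be interviewed as people in both HIV and MMT care "who also have elevated symptoms of depression, anxiety, or stress on the DASS-21". Sixteen are planned.

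The next group is family members, also 16. The rule has three parts:

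- Permission: "We will ask each patient if we may speak with their spouse, mother, or other primary household caregiver".
- Prior disclosure: "We will ask if they have disclosed their HIV and injection drug use status to that family member".
- Condition for contact: the team "will only approach the family member if the patient has disclosed to them and is willing for us to talk with them about these issues".

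On the content of the interviews, the same section says "We will present the FB protocol to 5 distinct groups", and relatives are one of the groups listed. Section 1.2 describes the Friendship Bench (FB) as a problem-solving intervention for common mental disorders.

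On confidentiality, Section 5.1.2 warns that disclosure of personal information, "particularly HIV, substance use disorder, and mental health status, may result in negative stigma being associated with the individual and/or family".

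**The concern.** The disclosure check exists because approaching a relative can itself give away something the patient has kept private. The protocol recognizes this for HIV and for injection drug use. It does not extend the check to mental health, although that is the criterion on which every Aim 1 patient is chosen and the subject of the program the relative is asked to comment on.

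At stake is the privacy of people whom Section 1.2 describes as highly stigmatized. What a relative has inferred cannot be taken back. The gap lies in a rule that is written down: a team that follows it exactly can still approach the relative of a patient who has never mentioned depression, anxiety or stress at home.

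**Working it through.** No arithmetic or stated figure is involved. The check is to set the sections side by side.

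| Status | Named as stigmatizing (5.1.2) | In the disclosure check (3.0, Aim 1) | Basis for selecting the patient | Subject of the FB intervention |
|---|---|---|---|---|
| HIV | yes | yes | yes | no |
| Substance use | yes | yes, as injection drug use | yes, through MMT care | no |
| Mental health | yes | **no** | **yes, all 16 of 16** | **yes** |

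The check covers two of the three named statuses. The missing one is the only one that is also the subject of the program presented.

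**Does the willingness clause fill the gap?** In "will only approach the family member if the patient has disclosed to them and is willing for us to talk with them about these issues", the closing words point back to what was just named, which is HIV and injection drug use. Nothing in the rule says the patient is told that the relative will hear about a mental health program.

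**Can prior disclosure of mental health be presumed?** No. Section 3.1 says screening for common mental disorders hardly occurs at these clinics. Some patients may first learn of elevated symptoms from the study's own DASS-21.

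**Following the rule for one patient.**

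1. The patient screens positive on the DASS-21 and is enrolled in Aim 1.
2. The patient has told a spouse about HIV and drug use, but not about low mood.
3. The patient permits contact and is willing to have HIV and drug use discussed. Every condition is met.
4. The spouse is invited because of this patient and is shown an intervention for common mental disorders.
5. The spouse may conclude that the patient has such symptoms.

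**Does another section stop this?** The precautions in Section 5.1.2 are coding of data, secure storage, restricted access and anonymizing of transcripts. None acts on what a relative learns by being contacted. The risk lists in Section 5.1.2 and the consent description in Section 5.1.5 address patients and health care providers. Neither mentions family members.

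**The case against.** **Permission is a real safeguard.** The patient can refuse the contact outright. The patient is also an Aim 1 interviewee to whom FB is presented, and Section 5.1.5 says consent will explain the purpose of the research. Many patients will understand what the relative would be asked about. This stands and lowers the risk. It does not close the gap, because the rule ties willingness to HIV and drug use and does not say the patient is told about the mental health content.

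**Disclosure is not certain.** A reader might infer that the interview tells the relative the patient's status. The documents do not say so. They do not have the relative told the DASS-21 result or the reason for selection, and FB could be introduced as a general clinic program. This stands: the supported statement is that the relative may infer it.

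**The consent forms and recruitment scripts cannot be judged.** They are not in the text available for review and may already deal with the point. This stands as a limit. The protocol rule would still need to agree with them.

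**Timing.** Section 3.3 schedules Aim 1 for July 2020 to March 2021, and Version 3.0 is dated 1 October 2023. The gap is 9 + 12 + 9 = 30 months. On those dates, rewording the rule protects nobody already interviewed. This stands, and it changes what the fix can achieve.

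**Two stronger readings.** A reader might infer that a site following the rule causes a breach that Section 5.2 requires to be reported at once. An inference drawn after a contact the patient permitted is not plainly a breach in that sense. A reader might also infer the same gap in Section 4.0, where the study collects "detailed locator information for the participant as well as for up to three individuals who could help reach the participant". That section does not say what those contacts would be told. This is silence, not a rule that lets an undisclosed patient through, so it is not part of this point.

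**Conclusion.** The rule in Section 3.0, Aim 1, is incomplete by the protocol's own standard. It checks two of the three statuses that Section 5.1.2 treats as stigmatizing and omits mental health, which all 16 index patients share by selection. Followed as written, it can let a relative infer the patient's mental health status.

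The size is bounded by the 16 planned family interviews. How many patients would have disclosed HIV and drug use but not mental symptoms is not given, so no expected number can be stated. The conclusion assumes that the willingness clause refers only to the two statuses named before it, and that no unseen script or consent form already covers mental health.

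The point concerns participant protection in the formative work. It has no effect on the trial's sample size, outcomes or analysis.

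**What to change.** In Section 3.0, Aim 1, use one of two wordings:

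- The relative is approached only if the patient, having been told that the interview concerns a mental health program, agrees to discussion of mental health as well as HIV and drug use.
- Relatives are approached and interviewed in a way that reveals neither the patient's screening result nor why the patient was selected.

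The first asks for informed agreement, not for earlier disclosure of symptoms, because a patient newly identified by the study screen may have had nothing to disclose. With either wording, add disclosure through contact with a relative to the risks in Section 5.1.2.

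The cost is a few words in the protocol and the recruitment script. Some patients may decline the family interview and need replacing. The documents do not allow that number to be estimated, but few are expected out of 16.

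If Aim 1 was completed on the planned dates, the sponsor should check which script was used with patients and relatives, correct the current text, and carry the corrected rule into the follow-on trial.
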